simplified severity score calculated as the MAP multiplied by the FiO₂. The RSS is used in place of the oxygenation index (OI) owing to the infrequent availability of data on the partial pressure of arterial oxygen (PaO₂) in hospitalized infants. The RSS correlates well with OI in infants receiving mechanical ventilation and is a useful predictor of poor respiratory outcomes in preterm infants.⁹²⁻⁹⁴ FiO₂ and MAP values (measured by the mechanical ventilator and reported on the ventilator graphical interface), are recorded at least hourly in the respiratory flow sheet in the electronic medical record (EPIC). These data will be used to calculate daily, time-weighted values for FiO₂, MAP, and RSS. Longitudinal change in these respiratory support measures during the 14-day study period will be compared (1) between infants who participate in the phase 1 trial and those enrolled in the observational (non-treated) cohort, and (2) among participants in the phase 1 trial, stratified by the administered dose of inhaled tobramycin.

Owing to the expected heterogeneity in lung disease and respiratory support requirements of the enrolled infants, a protocolized ventilator management algorithm will not be utilized during this study. However, routine practice in our unit is to wean FiO₂ in infants with BPD to maintain SpO₂ \geq 90%. Most infants with BPD who require invasive respiratory in our unit are supported using a time-cycled, pressure-limited, volume-guarantee mode of ventilation that delivers 8-10mL/kg of tidal volume at mandated rates of 15-25 breaths per minute. The Draeger V500 ventilator is used in all infants receiving acute care in the CHOP N/IICU who are prescribed intermittent mechanical ventilation. On this mode of support, the ventilator automatically adjusts the positive inspiratory pressure (PIP) – within set limits – to deliver the goal tidal volume. Change in the PIP along with any clinical adjustments in the positive end expiratory pressure (PEEP) will be the primary determinants of any observed changes in the delivered MAP. Only infants with an endotracheal tube leak ≤20% will be enrolled in this trial to avoid ventilator leak compensation and artificial inflation of the PIP levels.⁹⁵ Of note, the Draeger V500 ventilator calculates the endotracheal leak proportion during all modes of intermittent ventilation employed in our unit.

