Tracheal aspirate cytokine levels	Yes	No	 Individual cytokine levels measured pre-trial, ≤48 hours after the final dose, and 14 days after the final drug dose will be summarized. Transformation (e.g. logarithmic) or categorization by centiles will be considered based on the data distribution. Correction for total protein levels in the tracheal aspirate will be employed to account for differences in dilution during sample collection. The relative intra-patient change for the individual cytokine levels 	
			 from pre-trial baseline to the 2 post-trial timepoints will be calculated and compared between dose levels. The association between change in cytokine levels and tobramycin dose will be explored using bivariate and multivariate correlation analyses with Bonferroni correction for multiple testing.¹⁰⁰ We will consider exploratory cluster and linear discriminate analyses to identify airway immunological profiles associated with differences in the response to inhaled tobramycin (e.g. change in CFU/mL).^{101,102} 	
Respiratory support measures Hypoxemia (SpO ₂ <80%)	Yes	Yes	 Continuously recorded FiO₂, MAP, and RSS values will be converted to time-weighted daily averages for each study day. Continuously recorded SpO₂ data will be used to calculate daily rates of intermittent and prolonged hypoxemia and daily total hypoxemia exposure. Assessment of longitudinal change using linear mixed effects models will be considered. 	
Pulmonary mechanics	Yes	Yes	 Infants in both study cohorts will undergo pulmonary mechanics measurements pre-trial, after 7d, and after 14d. Intra-patient change, relative to pre-trial baseline, will be calculated for each participant and compared (1) between the two cohorts and (2) stratified by drug dose. Assessment of longitudinal change using linear mixed effects models will be considered. 	

Table 7. Planned statistical techniques and data availability for the phase 1 trial outcomes

CFU, colony forming units; GNR, Gram-negative rod; TA, tracheal aspirate

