We will *consider* constructing exploratory linear mixed effects models to evaluate the longitudinal change in repeated measures outcome data. Owing to the modest total study sample size and low numbers of infants treated with each tobramycin dose, these analyses will only be performed on an exploratory basis if graphical evaluations of the study data suggest strong evidence of a linear change over the course of the study period. These models will be considered: (1) for the phase 1 trial participants as a whole, (2) with stratification by the administered dose of inhaled tobramycin, and (3) between infants who participate in the phase 1 trial and those enrolled in the observational (non-treated) cohort (for the study outcome data collected in both cohorts). Treatment dose group and treatment week will be included in the models as independent variables (the latter is added to account for natural fluctuation in disease acuity over time). Random effects for intercept +/- slope will be considered based on their effect on model fit assessed using the Akaike information criterion. Backwards, stepwise elimination techniques to determine inclusion of possible confounding, independent covariates will be employed to account for measured differences between comparison groups. Adherence to accepted numbers of independent covariates based on the study sample size will be used to avoid model over-fitting.⁹⁸ If longitudinal models are performed, 95% confidence intervals for all estimates of effect will be reported and caution will be urged when interpreting these hypothesis generating results.

Patterns in the airway microbiome will be assessed by comparing (pre vs. post treatment) measures of alpha diversity (e.g. species counts, Shannon index) and beta-diversity (Weighted and unweighted UniFrac distances⁹⁹). Principal coordinate analyses and evaluation of dominant taxa will also be used to compare the microbiome before versus after completing treatment and with stratification by the administered dose of inhaled tobramycin. Linear mixed effects models, appropriate for repeated measures data, will also be constructed to measure the association between the dose of inhaled tobramycin and measures of alpha diversity.

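### Section 6.3.3 lets AIC drop the random slope and names no residual correlation or small-sample degrees of freedom, so within-dose intervals for time trends may be too narrow

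*Combined protocol and SAP*

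**What the plan says.** Section 6.3.3 leaves open the option of "constructing exploratory linear mixed effects models to evaluate the longitudinal change in repeated measures outcome data". Three uses are listed: all trial infants together, by dose level, and trial against observational cohort. On the fixed part it says "Treatment dose group and treatment week will be included in the models as independent variables", and on the random part "Random effects for intercept +/- slope will be considered based on their effect on model fit assessed using the Akaike information criterion". Table 7 repeats for respiratory support, hypoxemia and pulmonary mechanics: "Assessment of longitudinal change using linear mixed effects models will be considered".

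The FiO2, MAP and RSS data are daily. Section 5.3 says "These data will be used to calculate daily, time-weighted values for" these three measures, and Table 7 says the "values will be converted to time-weighted daily averages for each study day". Hypoxemia is also summarised by day.

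The plan limits the role of the models. Because numbers are small, "these analyses will only be performed on an exploratory basis if graphical evaluations of the study data suggest strong evidence of a linear change". If they are fitted, "95% confidence intervals for all estimates of effect will be reported and caution will be urged when interpreting these hypothesis generating results".

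Section 6.3.3 does not state a residual covariance structure, a degrees-of-freedom method, a significance level, or a rule for concluding that a change has occurred.

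**The concern.** Daily FiO2, MAP, RSS and hypoxemia counts in one ventilated infant are likely to resemble those of the day before. A run of correlated days can look like a trend when the average is not changing. A random slope absorbs part of this, because each infant's apparent trend then counts as one observation. If the slope is dropped and residuals are independent, 3 infants with 14 days each are treated as 3 × 14 = 42 separate readings around the infant means, and the standard error of the time effect is too small.

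AIC has little information with 3 to 6 infants and will often drop the slope when it is needed. Even when the slope is kept, a normal-based interval ignores that its variance is estimated from very few infants. At stake is a chance movement in a handful of infants being reported, with a 95% interval excluding zero, as a dose-specific trend that later trial design might use.

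**Working it through.** **Plan's own figure.** None exists for these models. The only power statements, in section 6.4, concern a two-group comparison of mean daily hypoxemic events. They reproduce: with SD 9 and a difference of 0.15 × 75 = 11.25, 12 against 12 gives 83.3% power (t); with 0.11 × 75 = 8.25, 24 against 24 gives 87.5%. Both exceed the stated 80%, and neither bears on the mixed models.

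**Inputs from the documents.** Up to 14 daily values per infant (sections 5.3 and 6.3.3); 3 to 6 infants per dose and up to 24 in total (sections 3.3.2 and 6.4); time entered as treatment week; random intercept with or without slope by AIC; 95% intervals.

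**Assumptions, not in the documents.** Residuals are fitted as independent. True daily residuals follow a first-order autoregression with correlation ρ of 0, 0.3, 0.5 or 0.7. The intercept SD is 2 residual SDs. There is no average change and, in the main runs, no true slope variation. The graphical condition is not applied.

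**Method.** For infant i on day t, y(i,t) = μ + a(i) + e(i,t), with corr[e(i,t), e(i,t+1)] = ρ. Both models are fitted by REML, the slope is kept if its AIC is lower, and the interval is estimate ± 1.96 × SE. The comparator is one least-squares slope d(i) per infant with interval mean(d) ± t(0.975, n−1) × SD(d)/√n. There are 1,500 datasets per setting, so the Monte Carlo standard error is √(0.05 × 0.95/1500) = 0.6 points at 5% and √(0.2 × 0.8/1500) = 1.0 point at 20%.

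Percentage of null datasets whose 95% interval excludes zero, time coded as week:

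| n | ρ | AIC choice, ±1.96 SE | AIC keeps slope | Intercept only, ±1.96 SE | Slope always kept, ±1.96 SE | Per-infant slope, t(n−1) |
|---|---|---|---|---|---|---|
| 3 | 0 | 5.2 | 5.7 | 5.5 | 3.1 | 5.4 |
| 3 | 0.3 | 10.9 | 15.4 | 13.1 | 5.8 | 4.5 |
| 3 | 0.5 | 17.8 | 30.0 | 23.7 | 11.6 | 5.1 |
| 3 | 0.7 | 19.6 | 51.8 | 32.1 | 13.0 | 4.0 |
| 6 | 0 | 4.8 | 6.6 | 5.0 | 2.9 | 4.7 |
| 6 | 0.3 | 11.3 | 23.6 | 13.6 | 6.9 | 5.5 |
| 6 | 0.5 | 13.1 | 49.5 | 21.6 | 8.1 | 5.3 |
| 6 | 0.7 | 14.0 | 74.5 | 31.5 | 11.2 | 5.7 |

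(The fourth column is the percentage of datasets in which AIC retained the slope.)

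With time coded as day, the AIC-chosen model gives 13.0, 18.5 and 22.3% at n = 3 and 13.2, 12.5 and 11.7% at n = 6, for ρ = 0.3, 0.5 and 0.7. Over both codings the range is 10.9% to 22.3%.

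**Which component matters.**
- AIC dropped the slope in about 48% to 85% of datasets at n = 3 and 22% to 76% at n = 6 (ρ = 0.3 to 0.7, both codings).
- Always keeping the slope but using ±1.96 SE still gives 5.8% to 16.1%.
- Keeping the AIC step but using t with n−1 degrees of freedom when the slope is retained gives 8.7% to 20.1%.
- So neither change is enough alone. In a 400-dataset grid with time as day, always keeping the slope with t(n−1) gave 0 to 4.2% at n = 3 and 2.2% to 6.2% at n = 6 for ρ = 0.3 to 0.7, which is conservative at n = 3. Kenward-Roger and Satterthwaite were not simulated.

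**Other settings.** True slope variation of 1 residual SD over the period, with ρ = 0 or 0.5, gives 11.2% to 20.2% at n = 3 to 6. Pooling 12 or 24 infants gives roughly 4% to 12% in the 400-dataset grid. The per-infant slope method stays between 3.9% and 5.8% in every 1,500-dataset setting.

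**The case against.** The strongest reply is that the plan already treats these models as weak evidence. They are optional, fitted only if graphs look strongly linear, and labelled hypothesis generating. Section 6.3.3 first applies paired tests of baseline against later values, which use one difference per infant and avoid the problem. Entering dose group as a covariate also suggests one model pooled over doses, where the inflation is smaller.

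Much of this stands. The wording on stratification by dose is ambiguous, and the larger figures apply only if separate within-dose fits are meant. The paired tests are sound on this point, but they compare single time points and do not supply the trend interval. A call for caution does not widen an interval that is too short. The graphical condition lowers the share of all null datasets that yield such an interval but raises the share among the models actually fitted. That selection would affect any method, including the one proposed here.

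A reader might infer that the plan assumes independent daily errors. It does not say so; it is silent, and independence is only the usual software default. A reader might also infer that a change over time will be declared at an inflated 5% level. The plan sets no test, level or decision rule for these models, so the percentages describe only how often a reported 95% interval would exclude zero.

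**Conclusion.** The concern holds as a gap in specification. With AIC free to drop the slope, residuals fitted as independent and normal-based intervals, a nominal 95% interval for a within-dose trend would exclude zero in about 11% to 22% of null datasets at n = 3 to 6. This rests on an assumed day-to-day correlation of 0.3 to 0.7. At zero correlation and with no slope variation the rate is about 5%.

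AIC selection should not be read as the sole cause: the missing small-sample degrees of freedom contribute as well. Nor does the point reach the trial's main conclusion, because dose escalation and the maximum tolerated dose rest on the toxicity composite. Pulmonary mechanics has three time points, so the daily-correlation argument does not apply there. Severity: minor.

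**What to change.** In section 6.3.3 and the matching rows of Table 7:

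- For within-dose and whole-cohort change in FiO2, MAP, RSS and hypoxemia, compute one least-squares slope (or week-2 minus week-1 mean) per infant and report a t interval on n−1 degrees of freedom.
- If a mixed model is fitted to pooled data, keep the random slope without AIC selection and use Kenward-Roger or Satterthwaite degrees of freedom. Autoregressive residuals may be named as an option.

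This takes about two sentences and no new data. The cost is wider within-dose intervals. For the same standard error, the multiplier rises from 1.96 to t(0.975, 2) = 4.30 at n = 3, a factor of 4.30/1.96 = 2.2, and to t(0.975, 5) = 2.57 at n = 6, a factor of 2.57/1.96 = 1.3. That width reflects what 3 to 6 infants can show about a trend.

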6.4 Sample Size and Power

The traditional 3+3 design is the prevailing method for conducting phase 1 drug trials.^{103,104} The sample size for this design is dictated by the number of different dosages investigated in the trial and whether or not additional patients are added to individual dosage levels based on the occurrence of a toxic drug response. Up to 24 infants are expected to provide analyzable trial data as described in section 3.3.2. The purpose of the 3+3 trial design is to continue dose escalation (within set boundaries) until at least two patients among a cohort of three to six patients experience dose-limiting toxicities (i.e., \geq 33% of patients with a doselimiting toxicity at that dose level).^{103,104} If the 300mg dose level is completed in 3 participants and none show evidence of a toxic response, up to 3 additional infants will be enrolled to receive to receive 300mg. The trial will be stopped if 2 of the additional infants receiving 300mg develop a toxic response and the 216mg dose will be used as the maximum tolerated dose in subsequent trials.

Enrollment in the observational cohort will run concurrent with enrollment in the phase 1 trial. A minimum of 12 infants and a maximum of 28 infants will be enrolled in the observational cohort. This variable enrollment number is selected to avoid delay in study closure if enrollment in the trial cohort out paces the observational cohort. Importantly, these numbers are anticipated to provide adequate statistical power to measure clinically meaningful differences in the frequency of intermittent hypoxemia, an important measure of cardiorespiratory stability.^{96,97} Premature infants with BPD average 75 (SD \pm 9) intermittent hypoxemic events (SpO₂ <80% for 10s-3min) per day during the first several months of life.^{105,106} A sample size of 12 infants in the observational cohort and 12 in the trial cohort will provide >80% power (α =0.05) to detect a 15% difference in the mean daily frequency of intermittent hypoxemic events between the two groups. A sample size of 24 infants per group will provide >80% to detect an 11% difference in in the mean daily frequency of intermittent hypoxemic events.

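### If the exploratory mixed models are fitted, backward elimination can drop real confounders from the between-cohort comparison, and the reported 95% intervals ignore the selection

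*Combined protocol and SAP*

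**What the plan says.** Section 6.3.3 of the combined protocol and SAP allows linear mixed models for the repeated-measures outcomes: for treated infants as a whole, by dose, and for treated infants against the observational cohort. They are conditional: "these analyses will only be performed on an exploratory basis if graphical evaluations of the study data suggest strong evidence of a linear change".

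Two terms are fixed: "Treatment dose group and treatment week will be included in the models as independent variables". Other covariates are left to the data: "Backwards, stepwise elimination techniques to determine inclusion of possible confounding, independent covariates will be employed to account for measured differences between comparison groups". On model size the plan says: "Adherence to accepted numbers of independent covariates based on the study sample size will be used to avoid model over-fitting". It gives no number, and the reference cited there (98) is, by its title, about events per variable in logistic and Cox regression. On reporting: "95% confidence intervals for all estimates of effect will be reported and caution will be urged when interpreting these hypothesis generating results".

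The section names no candidate covariates, no rule for removal and no confounder that always stays. The Akaike criterion appears, but only for choosing random effects. Nothing adjusts the intervals for selection.

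Section 6.4 gives the sizes: "A minimum of 12 infants and a maximum of 28 infants will be enrolled in the observational cohort", and "Up to 24 infants are expected to provide analyzable trial data as described in section 3.3.2". Section 9.1 states that there is no randomisation. Sections 4.1 and 9.6 leave the choice of cohort to the family.

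**The concern.** Backward elimination, as usually applied, asks how well a covariate predicts the outcome in the sample at hand. Confounding depends as well on how far the covariate differs between cohorts. In a few dozen infants a real confounder can easily fail a significance or AIC-type test and be removed, and its share of the cohort difference then stays in the estimated drug effect. The final interval also treats the selected model as if it had been known beforehand.

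Between-cohort comparisons are secondary objectives (section 2.2). Section 6.4 justifies the cohort sizes by power for one such comparison, and sections 1.7 and 9.4.3 say that the data will inform later trials. The other between-cohort tests in section 6.3.3 are unpaired and unadjusted, so this is the only confounder adjustment described.

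**Working it through.** **1. The plan's own figure.** Section 6.4 gives a mean of 75 intermittent hypoxemic events per day, SD 9. Power is approximately Φ(d√(n/2) − 1.96), two-sided alpha 0.05 assumed.

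- 12 v 12, 15% difference: 0.15 × 75 = 11.25; d = 11.25/9 = 1.25; 1.25 × √6 = 3.06; power 86.5% (83.3% with the t distribution).
- 24 v 24, 11% difference: 0.11 × 75 = 8.25; d = 0.917; 0.917 × √12 = 3.18; power 88.8% (87.5% with t).

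Both exceed 80%, as stated. This is an unadjusted comparison. The documents give no figure for the selection step, so what follows rests on assumptions.

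**2. Set-up.** The outcome is a cohort effect plus the sum of slope × covariate plus noise, with each confounder shifted by a gap between cohorts. Without adjustment the bias is number × gap × slope. Cohort is forced in; covariates are removed at p above 0.05, or above 0.157 (AIC-like). The check is how often the usual 95% interval contains the true cohort effect.

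**3. Eight candidates, three real confounders** (gaps 0.3-0.5 SD, slopes 0.2-0.5 SD, removal at 0.05, one value per infant, 3,000 data sets per setting):

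| Infants | Coverage |
|---|---|
| 12 v 12 | 84.5-90.0% |
| 18 v 20 | 86.3-91.7% |
| 24 v 28 | 87.6-92.9% |

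At 12 v 12, 44-84% of the real confounders were dropped. A repeat at p 0.157 gave 86-89%. With weak confounding at 12 v 12, elimination covered 89.5%, below the 93.2% with no adjustment at all.

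**4. Bias and width separated.** Here the candidates are only the real confounders, at 28 v 24, gap 0.5 SD, slope 0.4 (2,500 data sets each):

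| Confounders | Removal p | Kept | Coverage | Bias left | Reported SE / true SD |
|---|---|---|---|---|---|
| 2 | 0.05 | 77% | 91.9% | 0.05 | 0.91 |
| 2 | 0.157 | 89% | 94.2% | 0.02 | 0.96 |
| 3 | 0.05 | 76% | 90.0% | 0.07 | 0.86 |
| 3 | 0.157 | 89% | 93.0% | 0.02 | 0.92 |

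For three confounders the unadjusted bias is 3 × 0.5 × 0.4 = 0.60. Elimination at 0.05 leaves 0.07/0.60 = 12% of it, and the standard error is 14% too small. Both faults contribute. With no gap between cohorts, coverage is about 95% at 28 v 24 and 92-93% at 12 v 12.

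**5. Small candidate pool.** With two candidates and p 0.157, coverage is 93-94% at 12 v 12 and 94-95% at 28 v 24. At p 0.05 it is 91-93% and 92-94%.

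**6. Repeated measures.** A random-intercept model on 14 daily values, with three confounders, a harsher gap of 0.8 SD, slope 0.4 and p 0.05, covered 79% at 12 v 12 (300 data sets) and 88% at 28 v 24 (200). Keeping all three covariates gave 95% and 97%. The direction is the same.

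**7. The remedy tested.** Coverage near 95% for a fixed list arises when the list holds exactly the real confounders. A three-variable list with only one real confounder covered 86-96% at 12 v 12. At 28 v 24 it covered 72-94%, against 89-94% for elimination. The baseline value plus two irrelevant covariates covered 82-92% at 28 v 24, often below elimination. Forcing in a baseline confounder never lowered coverage in the settings tried.

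**The case against.** - **The models are optional and labelled.** They are only to be considered, after graphs show a strong linear trend, and are reported as hypothesis generating. This stands and limits the weight of the point. A general caution does not, however, tell a reader that a nominal 95% interval may cover 85-92%.
- **The removal rule is assumed.** The plan does not say that covariates go by significance. Its stated purpose would also fit a change-in-estimate rule, which was not simulated. This stands: the figures are conditional on the two thresholds tried.
- **The covariate cap helps.** If it limits the candidate pool, the shortfall shrinks, as step 5 shows. The plan does not say whether the cap applies to candidates or to final terms, and gives no number.
- **The simulated target is simpler than the planned one.** Most runs use one value per infant. The plan names group and week but no interaction, so the group coefficient is an average difference, which the runs do address. If slopes are to be compared instead, these figures do not carry over directly.
- **A fixed list can be worse.** Step 7 confirms this when the list misses the main confounders. What survives is the always-kept baseline value and the choice of the rest on clinical grounds.

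**Conclusion.** The point holds conditionally. If these models are fitted, backward elimination in this non-randomised comparison can discard real confounders, including the outcome's baseline value, and the intervals make no allowance for it. Coverage is roughly 85-92% at 12 v 12 and 87-95% at 28 v 24, through residual confounding and understated standard errors together. This rests on assumed gaps of 0.3-0.5 SD and removal at p 0.05 or 0.157. Stronger confounding gives lower figures (66% in the worst setting, with gaps up to 0.8 SD), but nothing in the documents shows confounding of that size.

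A reader might infer more than the documents support:

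- That both cohorts number 12-28. That range is the observational cohort's; the trial cohort is up to 24 evaluable infants.
- That false drug effects will be over-reported. This needs confounding in a consistent direction, which is unknown, and the plan labels the results as hypothesis generating.
- That a fixed list guarantees 95% coverage. It does not.
- That the dose-finding conclusion is at risk. The 3+3 decision (sections 6.3.2 and 6.5) uses none of these models.

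**What to change.** In section 6.3.3, replace backward elimination with a short covariate list, written down before outcome data are compared and kept whatever the p-values:

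- the baseline value of the outcome in every between-cohort model (the baseline record then serves as a covariate, not also as an outcome row);
- two or three entry variables judged on clinical grounds likely to drive both cohort choice and outcome, for example PMA and baseline RSS where RSS is not itself the outcome.

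Report the unadjusted estimate and one wider sensitivity model alongside. Do not claim 95% coverage for the adjusted intervals; say that they depend on the list containing the main confounders.

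The data are already planned: section 5.1.1.1 collects PMA and respiratory support at enrollment, and Table 1 schedules day 0 respiratory support and oximetry in both cohorts. No extra infants or visits are needed. The cost is wording and modestly wider intervals. At 12 v 12 the half-widths were about 0.95-1.00 SD with a fixed list against 0.83-0.91 SD with elimination. Comparing like ends of the ranges, 0.95/0.83 = 1.14 and 1.00/0.91 = 1.10, so about 10-15% wider.
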